### 7.0 Risks

Risks include those associated with routine blood draws – pain, redness, soreness, bruising, or infection may occur at the needle stick site. Rarely some people faint. We plan to offer EMLA cream to subjects prior to blood draws. A maximum of 4 blood draws will be obtained for procalcitonin testing in patients randomized to the intervention arm. Whenever possible, for PCT testing, we will use leftover blood from routine laboratory testing performed as part of ICU care.

Because PCT has not been well studied for making antibiotic modification decisions in children, there may be the risk of premature cessation of antibiotics. However, to prevent this from happening, all decisions to stop or continue antibiotic therapy will be made by the ICU attending physician, based on clinical judgement and standard of care studies such as bacterial cultures, WBC,CRP, and radiographic evaluations

The decision to start antibiotic treatment will in no way be affected by the study. In all subjects antibiotics will be started based on clinical suspicion of infection or microbiologic evidence of infection. This decision is at the discretion of the treating intensive care physician. Similarly, the decision to obtain PCT testing and/or adhere to the PCT algorithm or stewardship recommendations will be at the discretion of the ICU attending physician.

All subjects in both arms will have baseline audit of antimicrobial orders with feedback to providers by the antimicrobial stewardship team. For subjects in the intervention arm, the stewardship team will additionally recommend PCT testing and treatment, with recommendations to initiate or expand antibiotic use at PCT levels > 0.5 ug/L and to stop antibiotics when PCT levels decrease by >80% from peak concentration or to an absolute value < 0.25 ug/L.

Multiple studies to date have demonstrated that procalcitonin-guided antibiotic de-escalation algorithms are as safe as standard of care management in the adult ICU setting. As such, we do not anticipate increased risk of infection relapse rates or

increase in 30-day mortality between groups. These parameters will be monitored throughout the study and adverse events will be recorded and reported as detailed below.

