# **10.0 Statistical Considerations**

Based on data from studies evaluating PCT use among adult ICU patients, we estimate that median consumption of antibiotics will be 2.0 days less in the PCT group as compared to the control group. Assuming normal distribution, and a standard deviation of 6 days, a sample size of 125 patients per arm will provide at least 80% power to detect a difference in antibiotic duration of at least 2.0 days between study arms. These calculations are based on a chi-squared test with a two-sided Type 1 error rate of 0.05. Per clinical pharmacy data, the average duration of an antibiotic course per patient in VCH ICUs is 4 days, thus a difference of 2.0 days would be clinically significant.

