 - Patients who have initial procalcitonin levels <0.5 ng/mL versus >0.5 ng/mL

A. General Analysis Considerations

Data summaries and analyses will be presented by randomized arm.

To ensure participant confidentiality, listing of individual patient level data will be minimized as much as possible during study monitoring and for analyses. If such data are provided, they will be indexed with a unique blinded identifier or with identifiers removed. Study dates will not be presented, but provided as days/hours since randomization, as appropriate.

Participants who died prior to randomization, underwent bone marrow transplant or solid organ transplant prior to or after randomization, who are diagnosed with cystic fibrosis, or who ultimately are diagnosed with endocarditis, osteomyelitis, meningitis, mediastinitis or other invasive infection for which long duration of antibiotics is needed will be considered unevaluable for the primary outcome.

B. Statistical Monitoring Considerations

Routine statistical monitoring of accrual, study conduct, and data completion will be conducted by the statistical team and the study coordinator.

C. Monitoring Procalcitonin Algorithm Adherence

The study coordinator is responsible for monitoring intensive care unit provider adherence to the procalcitonin algorithm and, in the event of non-adherence, for soliciting reasons why they chose not to adhere to the algorithm.

D. Interim Analysis Considerations

The statistical team will perform an interim analysis when recruitment reaches 50% of goal accrual, to ensure safety of the procalcitonin-guided algorithm. Baseline characteristics such as age, sex and indication for antibiotics, primary outcome of overall DOT per patient within 14-days after randomization, and secondary outcomes of 30-day mortality and length of intensive care unit stay will be compared between groups.

E. Final Analysis Considerations

The primary analysis will be conducted when data from the last participant enrolled has been received.

The final analysis population will include participants who meet all eligibility criteria and no exclusion criteria.

The analysis will evaluate the primary, secondary, and exploratory outcomes in the procalcitonin-guided and control arms.

F. Analysis Plan

Statistical Considerations

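### The only planned between-arm safety look omits infection relapse, and restarting antibiotics is missing from the SAP's outcomes altogether

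*SAP*

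**What the plan says.** SAP section D schedules an "interim analysis when recruitment reaches 50% of goal accrual, to ensure safety of the procalcitonin-guided algorithm". The items compared between arms are baseline characteristics, the "primary outcome of overall DOT per patient within 14-days after randomization", 30-day mortality and ICU length of stay. The section gives no significance level or boundary, does not say what may follow from the look, and does not say who receives the results.

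Protocol section 7.0 names premature cessation of antibiotics as a risk of the study. Of safety it says "we do not anticipate increased risk of infection relapse rates" and, in the same sentence, no increase in 30-day mortality. It then adds: "These parameters will be monitored throughout the study and adverse events will be recorded". Specific Aim 2 lists recurrence of infection among the outcomes to compare between arms. The secondary outcomes in protocol section 6.0 include restarting antibiotics for a bacterial infection in the 30 days after they were stopped.

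The only error rate in either document is in protocol section 10.0: "a two-sided Type 1 error rate of 0.05". SAP section E places the primary analysis after the last participant's data have arrived, and SAP section F names a single primary test, the Wilcoxon rank-sum.

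**The concern.** The intervention works by encouraging earlier stopping, so its most direct possible harm is an infection that returns and needs treatment again. The protocol recognises this and pairs relapse with mortality. The SAP's safety look keeps mortality and drops relapse. The final SAP outcome list also lacks recurrence and restart of antibiotics. If the plan is followed as written, the trial could report shorter therapy and similar mortality without ever comparing the arms on the event that would show therapy had been stopped too soon.

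A second, smaller matter is that a look labelled as safety also compares the efficacy endpoint, and the plan does not say that this comparison carries no decision. The protocol has stewardship clinicians advising on both arms and in-person encouragement in one of them. It is therefore worth stating where the interim results go.

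**Working it through.** **1. The plan's own figure.** Inputs from protocol section 10.0: difference 2.0 days, SD 6 days, two-sided alpha 0.05, power at least 80%, 125 per arm.

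- n per arm = 2 × (1.960 + 0.842)² × 6² / 2² = 141.3, so 142.
- 125 per arm gives 75.0% power, so the stated figure does not reproduce.
- The SAP's 280, split evenly (assumed 140 per arm), gives 79.6%.

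That mismatch is a separate point. Here it matters only because half of goal accrual could mean 125 of 250 or 140 of 280, that is about 62 or 70 per arm. I use 70.

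**2. Where each safety outcome appears.**

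| Outcome | Protocol | SAP interim (D) | SAP final outcomes |
|---|---|---|---|
| 30-day mortality | 6.0, 7.0 | yes | yes (in-hospital) |
| ICU stay | 6.0 | yes | yes |
| Infection relapse or recurrence | Aim 2, 7.0 | no | no |
| Restart of antibiotics within 30 days | 6.0 | no | no |
| Hospital re-admission | not listed | no | yes |
| New hospital-acquired or multi-drug resistant infection | 6.0 (resistant organisms only) | no | yes |

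The last two rows are the nearest SAP neighbours to relapse, and neither is in the interim. SAP section B covers accrual, conduct and data completeness, and section C covers algorithm adherence. Section D is thus the only planned between-arm safety comparison before the end.

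**3. What a relapse comparison could show at 70 per arm.** The documents give no event rates, so these are assumptions. Power = Φ[(|p₁ − p₂| − 1.96 × √(2p̄(1 − p̄)/70)) / √((p₁(1 − p₁) + p₂(1 − p₂))/70)].

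| Assumed rates | Power |
|---|---|
| 3% v 6% | 13% |
| 5% v 10% | 20% |
| 10% v 20% | 38% |
| 5% v 15% | 50% |

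For 5% against 10%: (0.05 − 1.96 × 0.0445) / 0.0443 = −0.84, and Φ(−0.84) = 0.20.

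**4. The days-of-therapy comparison.** With two looks at information fraction 0.5, the test statistics have correlation √0.5 = 0.707. If p<0.05 at either look could count as success, type I error = 1 − P(|Z₁| < 1.96 and |Z₂| < 1.96) = 0.083. It is 0.086 at fraction 0.4 and 0.080 at 0.6. If only the final test can count, it is 0.05.

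Under the design effect, the interim Z has mean 2 / (6 × √(2/70)) = 1.972. The chance of p<0.05 at the look is then about Φ(1.972 − 1.960) = 50%. A nominally significant interim result is quite possible, which is why its status should be stated beforehand.

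**The case against.** **The look spends no alpha.** Section D limits its purpose to safety, section E runs the primary analysis after the last participant, and section F names one primary test. This stands. A reader might infer that the trial's type I error is 8.3%, but that figure needs a rule under which interim significance counts as success, and the SAP contains none. What remains is a missing clarifying sentence.

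**Comparing days of therapy by arm has a safety use.** The algorithm can lead to continuing or escalating antibiotics as well as stopping them, so exposure by arm helps in reading mortality and ICU stay. This also stands, and it is a reason to keep the comparison as descriptive.

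**Harm from early stopping is already monitored.** Protocol section 8.0 has adverse events recorded throughout, including harm when a PCT result leads to premature cessation, with expedited reporting. So it would be wrong to say that such harm goes unmonitored, and section 7.0 does not promise an interim comparison of relapse. But section 8.0 relies on case-by-case attribution by the investigator or treating providers. It is tied to a PCT result, and the study recommends PCT testing only in the intervention arm. That is not a comparison of arms.

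**The look is too small.** True for moderate differences, as shown above. The same limit applies to mortality, which is included.

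**Two further inferences the documents do not support.** One is that the interim result led to the change from 250 to 280. The documents do not say so, and 140 per arm simply brings power to about 80%. The other is that clinicians will see the trend. The SAP assigns the look to the statistical team and is silent on who receives the results.

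**Conclusion.** The relapse gap holds. An outcome that the protocol names as a risk, promises to monitor and lists as a secondary outcome is absent from the interim safety comparison and from the SAP's final outcomes. This rests on the text and needs no assumption about rates. The limited power at about 70 per arm rests on assumed event rates and an even split.

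On days of therapy, the conclusion is narrower: the plan should say that the comparison is descriptive. The 8.3% is a conditional upper bound. It assumes independent patients, whereas the SAP describes a cluster crossover design, and clustering is not allowed for here.

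The documents do not say whether the look has taken place. The SAP is dated 4 June 2019 and the protocol projects the study to end on 30 June 2019, so it may have.

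**What to change.** - Add restart of antibiotics for a bacterial infection, as the protocol defines it, to the section D comparison, and restore it to the SAP's final outcomes and tables. Adding it to the interim alone would leave the larger gap open.
- State the denominator and the follow-up. The SAP's stated duration is the hospital stay, or up to 30 days for those still in hospital, while the outcome runs for 30 days from stopping. A participant who stops on day 10 has a window to day 40. Ascertainment after discharge may be incomplete and should be reported by arm. Use all analysed participants as the denominator, because having stopped is itself affected by the algorithm.
- Note that about 70 per arm can reveal only large differences, so similar rates at the look are weak reassurance.
- State that the days-of-therapy comparison is descriptive, that no stop or design change for benefit can follow from it, and that the results stay with the statistical team. The final test then keeps two-sided 0.05.
- Say which total the 50% refers to, 250 or 280.
- If the look has already been done, record what was compared, who saw it and, if true, that no decision followed. The addition to the final analysis still applies.

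The cost is a short SAP revision, one more outcome to analyse, and some extra work on follow-up data after discharge.

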### 4.0 Inclusion/Exclusion Criteria

Eligible subjects will be identified on admission to an intensive care setting by monitoring daily ICU census in EPIC.

Subjects will be enrolled if they:

- Are prescribed or administered antibiotics in the hospital within 1 calendar day of enrollment.
- Are admitted to the pediatric ICU (units 5A or 5C)
- Have parents or legal guardians who provide informed consent, or provide consent themselves if 18 years of age or older
- Provide assent if >7 years of age

Subjects will be excluded if they meet any of the following criteria:

- Are not prescribed antibiotics in the hospital
- Receive intravenous antibiotics within 7 days prior to identification for study enrollment
- Primary or secondary immune deficiency
- History of malignancy, bone marrow transplant or solid organ transplant
- A diagnosis of cystic fibrosis
- Neonates < 34 weeks gestation
- Patients receiving treatment for endocarditis, osteomyelitis, meningitis, mediastinitis, or other invasive infection, for which long durations of antibiotics are needed.
- Do not provide informed consent/assent

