Table summaries will present the following study population characteristics by randomized arm. All variables, as noted below, will be analyzed on the continuous scale or as categories or both as appropriate.

For continuous variables, summary statistics will include # of participants and median (Q1-Q3).

For categorical variables, summary statistics will include number (%) for each category. In calculation of percentages, participants with missing data will not be included in the denominator.

We will calculate the median days of antibiotic therapy per patient within the first 14-days post randomization in both treatment arms, together with the interquartile range. The primary test will be a Wilcoxon rank-sum test without the assumption of normality.

We will compare other continuous outcomes using a Wilcoxon rank-sum test, and categorical outcomes using a Pearson's chi-squared test.

We will perform a post-hoc analysis using a multivariable ordinal logistic regression model to assess the association between randomization group and the overall antibiotic duration of therapy per patient, adjusting for sex, recent surgical procedure, antibiotic indication of possible sepsis, and fever, vasopressor support and need for mechanical ventilation at enrollment.

We will perform a Cox proportional odds model adjusting for location of enrollment and study day to evaluate the hazard ratio for time to cessation of antibiotics within 4-days and within 10-days.

Final Analysis Considerations

The primary analysis will be a modified intention to treat (ITT) analysis. Participants who died prior to randomization, underwent bone marrow transplant or solid organ transplant prior to or after randomization, who are diagnosed with cystic fibrosis, or who ultimately are diagnosed with endocarditis, osteomyelitis, meningitis, mediastinitis or other invasive infection for which long duration of antibiotics is needed will be considered unevaluable. These are all issues that would otherwise qualify as exclusion criteria at the time of enrollment.

1. Study Population

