1.2 Study Population Characteristics

Table: Demographics

- a. Current age on day of study entry (in years): Continuous
- b. Sex at birth: By category (male/female)
- c. Self-reported race, ethnicity and race/ethnicity as defined by NIH reporting standards: By category

2. Health Characteristics/Status at Entry

- a. In pediatric ICU or pediatric cardiac ICU at randomization
- b. Requirement for intravenous vasopressor agents (categorical, yes or no)
- c. Mechanical ventilation (categorical, yes or no)
- Fever (temperature >38.0 deg F) or hypothermia (temperature <35.0 deg F) (categorical, yes or no)
- e. Surgical procedure within 2 weeks prior to enrollment (categorical, yes or no)
- f. Presence of comorbidity
 - Heart disease
 - Gastrointestinal disease
 - Neurologic disease
 - Bone/joint infection
 - Renal disease
 - Hematologic disease
 - Oncologic disease
 - Pulmonary disease
 - Other
 - No comorbidities
- g. Indication for antibiotics
 - Concern for sepsis
 - Pneumonia
 - Meningitis/encephalitis
 - Urinary tract infection
 - Other
- h. Attending physician on the day of enrollment

• Choose 1 of 20 pediatric ICU attending physicians who wrote the progress note for the patient on the day of enrollment

3. Antibiotic Use

Table: Days of antibiotic therapy per patient within 14 days (PRIMARY OUTCOME). Patients who are continued on antibiotics longer than 14 days will be assigned a time of 14 days per antibiotic.

Table: Days of broad-spectrum antibiotic therapy per patient within 14 days. Patients who are continued on broad-spectrum antibiotics longer than 14 days will be assigned a time of 14 days per antibiotic.

Table: Count (%) of patients on any antibiotic longer than 72 hours

Table: Count (%) of patients on broad-spectrum antibiotics longer than 72 hours

Table: Count (%) of patients on IV antibiotics longer than 72 hours

Table: Count (%) of patients on 2 or more antibiotics at 24, 48, 72, and 96 hours after enrollment

Table: Days of IV antibiotic therapy per patient within 14 days. Patients who are continued on IV antibiotics longer than 14 days will be assigned a time of 14 days per antibiotic.

Figure: Time to first antibiotic modification, using the empirical cumulative distribution function.

Figure: Percent of patients on antibiotics within 14 days of enrollment, using a Cox proportional hazards model

4. Sensitivity and Additional Analyses of the Primary Endpoint

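### SAP section E and sections A/F describe the primary analysis set differently, in both directions, and the SAP does not say which rule governs or whether both apply

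*SAP*

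**What the plan says.** SAP section E first fixes the timing: "The primary analysis will be conducted when data from the last participant enrolled has been received". The next sentence gives the population: "The final analysis population will include participants who meet all eligibility criteria and no exclusion criteria".

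SAP section F has a subsection with the same title as section E. It opens: "The primary analysis will be a modified intention to treat (ITT) analysis". The removal list follows. Its first part reads: "Participants who died prior to randomization, underwent bone marrow transplant or solid organ transplant prior to or after randomization, who are diagnosed with cystic fibrosis". Its second part covers children who "ultimately are diagnosed with endocarditis, osteomyelitis, meningitis, mediastinitis or other invasive infection for which long duration of antibiotics is needed will be considered unevaluable". The subsection closes by saying that the listed items would have counted as exclusions at enrollment. SAP section A carries the same list and ties it to the primary outcome.

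Protocol section 4.0 has a longer list of exclusions. It includes "Primary or secondary immune deficiency" and "History of malignancy, bone marrow transplant or solid organ transplant", gestation below 34 weeks, and intravenous antibiotics in the 7 days before identification for the study.

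The flowchart in SAP 1.1 counts removals from the modified ITT set only and mentions no other analysis set.

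**The concern.** A SAP should let two programmers who work independently arrive at the same list of children for the primary test. Here one section defines the set by full eligibility and another by a specific list of removals. No sentence ranks the two or says that they are applied in sequence.

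The choice might be made with knowledge of the results. The stewardship team knows each child's arm, because it recommends PCT testing in one arm only. SAP section D also has the statistical team compare the primary outcome between groups at 50% of accrual. Nothing suggests that anyone would choose the set by its result, but the text leaves room to do so.

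The mismatch on the A/F side is a concern for a second reason. It removes children on events or diagnoses that arise after randomization, in an open-label trial of a diagnostic strategy. Such removals need not be balanced between arms.

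**Working it through.** No sample size, power or error rate enters this point. The check compares Protocol section 4.0 item by item with the A/F list, and then applies each possible reading of the SAP to a child who has already been enrolled.

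**On the protocol's exclusion list but not on the A/F list:** immune deficiency; malignancy; gestation below 34 weeks; intravenous antibiotics in the prior 7 days; no antibiotic prescribed; no consent or assent. The last two should seldom arise after enrollment. The first four can plausibly come to light late. The protocol puts malignancy and transplant in a single bullet; the A/F list takes transplant and leaves malignancy out.

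**On the A/F list but not clearly an exclusion at enrollment:** transplant after randomization; a long-course invasive infection diagnosed only later. Death before randomization is also listed, but such a child would not be in a randomized comparison anyway.

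| Enrolled child with | E alone | A/F list alone | Both applied |
|---|---|---|---|
| Malignancy, immune deficiency, gestation below 34 weeks, or prior IV antibiotics | out | in (not listed) | out |
| Transplant before enrollment, or known cystic fibrosis | out | out | out |
| Long-course infection under treatment at enrollment | out | out | out |
| Transplant after randomization | not clearly out | out | out |
| Long-course infection diagnosed later | not clearly out | out | out |

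The first row and the last two rows depend on the reading. The entry 'in' in the first row is an inference from absence: section F does not say that unlisted children are kept, and it does not say that the list is exhaustive.

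**The case against.** The strongest reply is that the rules are compatible. Section F never says that only the listed children are removed. Section E can be read as the overall population, with A/F as a further restriction for the primary outcome. The closing sentence of section F, which links its list to the exclusion criteria, suits that reading. This stands as far as it goes. A reader might infer that the two rules cannot both be followed, and the documents do not support that: the last column of the table shows that they can be. But the SAP does not state the nested reading, and the flowchart shows a single modified ITT step.

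A reader might also take the "Oncologic disease" row of the baseline table (SAP 1.2) as proof that children with malignancy are expected in the analysed set. It is weak evidence. The same table has rows for bone or joint infection and for meningitis or encephalitis, which overlap with section F's own removals. The table reads as a general checklist.

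A reader might try to size the effect as a shift in an arm mean. With 280/2 = 140 per arm, the protocol's 4-day average course, and k children at 14 days all in one arm, the shift is k × (14 − 4)/140. That gives 0.14 day for k = 2 and 0.43 day for k = 6, or 7% to 21% of the hypothesised 2 days. The documents do not support this figure. They give no value for k, no reason to place every such child in one arm, and no statement that these children have the longest courses. Nor is 14 a fixed value, since SAP 1.2 (Antibiotic Use) caps at 14 days for each drug. The primary outcome is also a median compared by Wilcoxon test, not a mean. Dropping the 6 highest of 140 values moves the median position from (140 + 1)/2 = 70.5 to (134 + 1)/2 = 67.5. That is 67.5/140, about the 48th percentile of the original arm, and on whole-day data the median might not change. The rank-sum statistic could still move, by an amount that the documents do not allow one to estimate.

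Lastly, the protocol exclusions are applied at screening, so the first row of the table reaches only children enrolled in error or found ineligible late. That limits the likely number. It does not remove the point, because the SAP itself plans for late-found ineligibility, and the last two rows do not depend on screening errors.

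**Conclusion.** The primary analysis set is not uniquely defined. Sections A and F give one rule and section E another; they differ in both directions, and the SAP states neither precedence nor combination. This is an ambiguity to close before the final analysis, not a demonstrated bias. The number of children affected and the effect on the primary comparison are unknown.

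The conclusion assumes that at least some enrolled children will be found ineligible late or will have a listed event after randomization. The SAP's own provision for such cases makes this reasonable, but the documents do not establish that any occurred.

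**What to change.** State one primary population and use the same wording in SAP sections A, E and F and in the flowchart. It should be all enrolled children, analysed as assigned. Any removals should be listed in full and limited to conditions established from information that existed before randomization. Making section F the sole definition as it now stands would not be enough, because it would keep the removals that depend on later events or diagnoses.

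Run the alternative set (children who satisfy every eligibility criterion, with the section F removals also applied) as a named sensitivity analysis. Report by arm how many children differ between the two sets, and why.

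The cost is a few sentences of text, one more analysis run and an added flowchart line. The downside is that a few children found ineligible late remain in the primary set; the sensitivity analysis shows whether that matters.

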1.1 Accrual

1. Figure (flowchart): Number of patients assessed for eligibility, number excluded and reasons for exclusion, number (%) who underwent randomization, number assigned to each group, number excluded from modified intention to treat analysis, number included in each arm for modified intention to treat analysis.

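### The SAP names no analysis population for mortality and the other clinical outcomes, and contradicts itself on whether its post-assignment exclusions reach beyond the primary outcome

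*SAP*

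**What the plan says.** Four places in the SAP bear on who is analysed.

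- **Section A, General Analysis Considerations.** Children with certain conditions "will be considered unevaluable for the primary outcome". The list includes those "or who ultimately are diagnosed with endocarditis, osteomyelitis, meningitis, mediastinitis or other invasive infection for which long duration of antibiotics is needed".
- **Section F, Final Analysis Considerations.** The paragraph opens "The primary analysis will be a modified intention to treat (ITT) analysis". It then repeats the same list, but the children on it now simply "will be considered unevaluable. These are all issues that would otherwise qualify as exclusion criteria at the time of enrollment". The restriction to the primary outcome is gone.
- **Section E, Final Analysis Considerations.** "The final analysis population will include participants who meet all eligibility criteria and no exclusion criteria". The next sentence reads "The analysis will evaluate the primary, secondary, and exploratory outcomes in the procalcitonin-guided and control arms".
- **Section 1.1, Accrual.** The flowchart runs from assessment to randomisation, to exclusion from the modified ITT set, and ends at the "number included in each arm for modified intention to treat analysis". It shows no other set.

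The Clinical Outcome Measures (30-day in-hospital mortality, hospital and ICU days, ventilation days, antibiotic-associated complications, new hospital-acquired infections or resistant organisms, re-admission) and the tables in SAP section 6 name no analysis set. The two stay outcomes are restricted to children alive at 30 days, but that is part of their definition. SAP section D compares 30-day mortality and ICU stay at half accrual as a safety check, also without stating a population.

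**The concern.** Aim 2 of the protocol tests whether clinical outcomes and safety are comparable between arms. Protocol section 7.0 names the hazard: "there may be the risk of premature cessation of antibiotics". The clinical tables are where a between-arm safety signal would appear.

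Under the section F wording combined with section E, an analyst could compute those tables after dropping children because of a diagnosis made after assignment. Only the intervention arm's management is directed by PCT results, so both the frequency of such diagnoses and the course of the children who receive them could differ by arm. An analyst who followed section A instead would keep these children. The plan does not say which is meant, so the choice could be made after the data are seen.

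The remaining clinical outcomes also carry more of the safety question than the protocol intended. Re-initiation of antibiotics for a bacterial infection within 30 days is a secondary outcome in the protocol but is absent from the SAP's outcome list.

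**Working it through.** The plan gives no figure on this point to reproduce. The check is a comparison of texts, followed by an illustration on assumed counts.

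**1. Scope of the exclusion.** Section A limits it to the primary outcome. Section F does not, although its paragraph is introduced as describing the primary analysis. Section E has no such limit: one population, filtered on exclusion criteria, serves primary, secondary and exploratory outcomes. The SAP lists mortality and ICU stay under a separate clinical heading, which might seem to put them outside section E. But SAP section D calls both of them secondary outcomes, and the protocol's Study Outcomes list them as secondary too. The documents therefore support two incompatible populations.

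**2. Is the rule just the enrolment criterion applied late?** Section F says the listed issues would have been exclusions at enrolment. Protocol section 4.0 excludes children already under treatment for these infections. The SAP removes children who are eventually diagnosed with one, with no cut-off date and with an open category of other invasive infections. The SAP rule is wider. It covers both an infection present at entry but recognised late, and one that arises or relapses after antibiotics are stopped.

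**3. Overlap with an outcome.** Clinical outcome 6 counts new hospital-acquired infections within 30 days. A new invasive one needing long treatment could be both an outcome event and a reason for removal.

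**4. Illustration.** Inputs: 140 per arm (the SAP's 280 split 1:1, an assumption), 4 deaths per arm among children who are kept (assumed), and assumed numbers removed *r* and deaths among them *d*.

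- Risk in all assigned children = (4 + *d*) / 140
- Risk after removal = 4 / (140 − *r*)

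| Removed, control / PCT | Deaths among removed, control / PCT | All assigned, control v PCT | Difference (points) | After removal, control v PCT | Difference (points) |
|---|---|---|---|---|---|
| 4 / 4 | 0 / 0 | 4/140 = 2.9% v 4/140 = 2.9% | 0.0 | 4/136 = 2.9% v 4/136 = 2.9% | 0.0 |
| 4 / 4 | 1 / 1 | 5/140 = 3.6% v 5/140 = 3.6% | 0.0 | 4/136 = 2.9% v 4/136 = 2.9% | 0.0 |
| 4 / 4 | 0 / 2 | 4/140 = 2.9% v 6/140 = 4.3% | +1.4 | 4/136 = 2.9% v 4/136 = 2.9% | 0.0 |
| 4 / 8 | 0 / 2 | 4/140 = 2.9% v 6/140 = 4.3% | +1.4 | 4/136 = 2.9% v 4/132 = 3.0% | +0.1 |
| 4 / 8 | 1 / 4 | 5/140 = 3.6% v 8/140 = 5.7% | +2.1 | 4/136 = 2.9% v 4/132 = 3.0% | +0.1 |
| 6 / 14 | 1 / 6 | 5/140 = 3.6% v 10/140 = 7.1% | +3.6 | 4/134 = 3.0% v 4/126 = 3.2% | +0.2 |

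Deaths among kept children are set equal by construction, so the table shows what a removal rule can conceal, not what is likely. Exchanging the arms would conceal a benefit instead. With balanced removals and balanced deaths among the removed (first two rows), nothing changes.

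**The case against.** The strongest reply is that no plan to drop these children from the safety outcomes is stated. Section A confines the rule to the primary outcome, and the section F paragraph opens by describing the primary analysis, so both can be read as primary-only. Section E filters on exclusion criteria, and a child who develops an invasive infection after enrolment did not meet the protocol criterion at entry. This reading is reasonable, and it rules out saying that the SAP intends to remove harmed children. It does not resolve the conflict: section F describes the later diagnoses as equivalent to exclusion criteria, section E removes anyone with an exclusion criterion, and no text assigns the clinical outcomes to another set.

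A reader might go further and infer that the listed infections are the harm that premature stopping would cause. The documents do not say so. Protocol section 7.0 refers to infection relapse and 30-day mortality, and the SAP lists meningitis/encephalitis among the indications at entry, which fits late recognition of the presenting illness. The sound criticism is that the rule cannot tell the two apart.

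A reader might also infer that every clinical comparison is biased towards similarity, or size the problem by the share of an arm's deaths that is lost. With 140 per arm, 4% mortality in kept children, 3–8% removed and 10–30% mortality among those removed, that share runs from 0.003/(0.04 × 0.97 + 0.003) = 7% to 0.024/(0.04 × 0.92 + 0.024) = 40%. All those rates are assumed, and a loss within one arm is not a change in the contrast between arms.

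Finally, safeguards exist. Protocol section 8.0 has all adverse events recorded and reported without any modified ITT filter, section 7.0 has relapse and mortality monitored throughout, and the flowchart will show how many were excluded. These limit the consequence, but they do not supply a population for the final between-arm tables.

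**Conclusion.** The point holds as an internal contradiction and an omission: the SAP gives two scopes for its post-assignment exclusions and no population for the clinical outcomes. It is not a stated decision to exclude harmed children.

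Bias in the Aim 2 comparison requires removals, or outcomes among those removed, to differ by arm, and the documents fix neither its direction nor its size. They give no mortality rate and no rate of later-diagnosed invasive infection. The tabulated shrinkage, from +1.4 to +3.6 points down to 0.0 to +0.2, rests wholly on assumed counts and on equal deaths among kept children. The change is a cheap improvement worth making, because it settles the population in advance and removes a possible bias from the safety comparison.

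**What to change.** - **SAP section F:** state that all clinical and safety outcomes, at both the interim and final analyses, are analysed in all assigned children by assigned arm. Keep the existing outcome definitions, including the restriction of the two stay outcomes to children alive at 30 days.
- **SAP sections A, E and F:** use one wording throughout that limits the unevaluable rule to the antibiotic-use outcomes.
- **SAP sections 1.1 and 6:** add the all-assigned set to the flowchart. Report children removed from the antibiotic-use analysis by arm, with reason, timing of diagnosis relative to assignment, and clinical outcome.

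The cost is SAP wording, one analysis flag and one short table. The only downside is small: a few children with planned long courses will add noise to length of stay.
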